
Primary Endpoint(s)
	
The primary safety endpoint is freedom from major adverse events (MAE) at 30 days or during hospitalization if this exceeds 30 days.
 
Major adverse events include death, bowel ischemia, myocardial infarction, paraplegia, renal failure, respiratory failure, and stroke.
 
The primary effectiveness endpoint is the proportion of the study subjects with treatment success at 1 year. Treatment success is defined as a composite of technical success and freedom from the following:
 
 ○ Aneurysm enlargement i.e., greater than or equal to 5 mm as compared to any previous CT measure using orthogonal (i.e., perpendicular to the centerline) measurements

	
 ○ Aneurysm rupture ○ Aneurysm-related mortality ○ Conversion to open repair ○ Secondary intervention for migration, Type I and III endoleaks, device integrity failure (e.g., fracture), and patency-related events (i.e., device component stenosis or occlusion and embolic events)

Secondary Endpoints
	
 • Technical success and the individual components of technical success: 
 ○ Successful delivery ○ Deployment at the intended implantation site ○ Patency of all endovascular graft and stent components ○ Absence of device deformations requiring unplanned placement of an additional device ○ Absence of inadvertent covering of aortic branch vessels ○ Successful withdrawal • Freedom from the individual components of the primary safety endpoint at 30 days: 
 ○ Death ○ Bowel ischemia ○ Myocardial infarction ○ Paraplegia

	
○ Renal failure○ Respiratory failure○ Stroke● Freedom from paraparesis at 30 days● The following at each follow-up interval:
○ Treatment success and the individual components of treatment success including freedom from the following:
– Aneurysm enlargement– Aneurysm-related mortality– Aneurysm rupture– Conversion to open repair– Secondary intervention for migration, type I and III endoleaks, device integrity failure (i.e., fracture), and patency-related events (i.e., device stenosis or occlusion and embolic events).– Renal failure– All-cause mortality– Endoleaks– Device integrity failure (e.g., fracture)
--	---

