3.2 Pathophysiology

Aortic aneurysm is a progressive disease characterized by structural deterioration, gradual expansion, and eventual potential for rupture of the aorta if left untreated. The definition of aortic aneurysm is a localized or diffuse dilatation encompassing all three layers of the aorta with diameter >50% larger than the expected normal aortic diameter.

An aneurysm which spans both the thoracic and abdominal cavities defines a thoracoabdominal aortic aneurysm. The expansion rate of thoracoabdominal aneurysms ranges from 2-4mm per year and

is not influenced by the size of the aneurysm at the time of diagnosis^{2,3}. The expansion rate of thoracoabdominal aneurysms does not appear to increase as individual aneurysms enlarge. The presence of COPD and hypertension are factors associated with an increased rate of enlargement^{4,5}. Thoracoabdominal aortic aneurysms become a risk for rupture if they are above 5.5-cm in diameter or if they are less than 5.5-cm in diameter and are growing more rapidly than 0.5-mm in 6 months. The 5-year survival of thoracoabdominal aneurysm patients ranges from 7-20% depending on the percentage of aneurysms secondary to aortic dissection^{3,6}. Half of the thoracoabdominal aneurysm deaths are attributed to rupture and the other half are due to some sort of comorbidity such as myocardial infarction. The overall survival of thoracoabdominal aortic aneurysm patients is often overestimated, because the patients with advanced comorbid medical illness are not included and account for 46-68% of the patients reported in past natural history studies^{3,6-9}. Dissecting aneurysms have a higher rate of rupture and have a worse prognosis without intervention.

Most patients with a descending thoracic or thoracoabdominal aneurysm do not have symptoms when first diagnosed^{7,10}. They are likely diagnosed with a CT scan for another disease. Some patients have vague chest, back, flank, or abdominal pain. The pain may increase in severity as the aneurysm enlarges, or it may be sudden due to rapid expansion and impending rupture. Symptoms can result from compression of or erosion into adjacent intra-thoracic structures or bony thorax^{7,11,12}. Hoarseness from stretching or compression of the left recurrent laryngeal nerve, tracheal deviation, persistent cough, or other respiratory symptoms are sometime seen. Patients with a thoracoabdominal aortic aneurysm may have a palpable pulsatile mass in the upper abdomen.

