4.4.2 Eligibility Criteria

Primary Study Arm

Inclusion Criteria

- A patient may be entered into the study if the patient has at least one of the following:
 - An aneurysm with a maximum diameter of greater than or equal to 5.5 cm or 2 times the normal diameter just proximal to the aneurysm using orthogonal (i.e., perpendicular to the centerline) measurements
 - Aneurysm with a history of growth greater than or equal to 0.5 cm in 6 months
 - Saccular aneurysm deemed at significant risk for rupture
 - Symptomatic aneurysm greater than or equal to 4.5 cm
- Axillary or brachial and iliac or femoral access vessel morphology that is compatible with vascular access techniques, devices or accessories, with or without use of a surgical conduit
- Proximal landing zone for the thoracic bifurcation stent graft that has:
 - Greater than or equal to 2.5 cm of non-aneurysmal aortic segment including previously placed graft material (neck) distal to the left subclavian artery (LSA) and diameter in the range of 26-42 mm

- Adequate distance from the celiac artery, in order to accommodate cannulation from the antegrade access point when considering the total deployed length of the thoracic bifurcation and visceral manifold
- Iliac artery or aortic distal fixation site, including both native tissue and previously placed graft, greater than or equal to 15 mm in length and diameter in the range of 8 – 25 mm
- Age: greater than or equal to 18 years old
- Life expectancy: greater than 1 year

Exclusion Criteria

General exclusion

- Patient is a good candidate for and elects for open surgical repair
- Can be treated in accordance with the instructions for use with a legally marketed endovascular device
- Is eligible for enrollment in a manufacturer-sponsored IDE at the investigational site
- Unwilling to comply with the follow-up schedule
- Inability or refusal to give informed consent
- Urgent or emergent presentation
- Patient is pregnant or breastfeeding
- Patient has a contained rupture
- Patient has a ruptured aneurysm
- Patient has a dissection in the portion of the aorta intended to be treated
- Obstructive stenting of any or all of the visceral vessels

- Poor performance status including two major system failures (including but not limited to cardiovascular, pulmonary, renal, hepatobiliary, and neuromuscular)

Medical exclusion criteria

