4.4.3 Study Endpoints

The primary safety endpoint is freedom from major adverse events (MAE) at 30 days or during hospitalization if this exceeds 30 days.

Major adverse events include death, bowel ischemia, myocardial infarction, paraplegia, renal failure, respiratory failure, and stroke.

The primary effectiveness endpoint is the proportion of the study subjects with treatment success at 1 year. Treatment success is defined as a composite of technical success and freedom from the following:

- Aneurysm enlargement i.e., greater than 5mm as compared to any previous CT measure using orthogonal (i.e., perpendicular to the centerline) measurements
- Aneurysm rupture
- Aneurysm-related mortality
- Conversion to open repair
- Secondary intervention for migration, Type I and III endoleaks, device integrity failure (e.g., fracture), and patency-related events (i.e., device component stenosis or occlusion and embolic events)

Secondary endpoints include:

- Technical success and the individual components of technical success:
 - Successful delivery
 - Deployment at the intended implantation site
 - Patency of all endovascular graft and stent components
 - Absence of device deformations requiring unplanned placement of an additional device
 - Absence of inadvertent covering of aortic branch vessels
 - Successful withdrawal

- Freedom from the individual components of the primary safety endpoint at 30 days:
 - Death
 - Bowel ischemia
 - Myocardial infarction
 - Paraplegia
 - Renal failure
 - Respiratory failure
 - Stroke
- Freedom from paraparesis at 30 days
- The following at each follow-up interval:
 - Treatment success and the individual components of treatment success including freedom from the following:
 - Aneurysm enlargement
 - Aneurysm-related mortality
 - Aneurysm rupture
 - Conversion to open repair
 - Secondary intervention for migration, type I and III endoleaks, device integrity failure (i.e., fracture), and patency-related events (i.e., device stenosis or occlusion and embolic events).
 - Renal failure
 - All-cause mortality
 - Endoleaks
 - Device integrity failure (e.g., fracture)

- Patency-related events (i.e., device stenosis or occlusion and embolic events)
- Other device-related events

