4.9 Definitions

Aortic aneurysm enlargement: ≥ 5 mm as compared to any previous CT measure using orthogonal (i.e., perpendicular to the centerline) measurements

Aortoiliac aneurysm: aneurysm of the abdominal aorta and including one or both of the iliac arteries

Aneurysm-related mortality:

Death occurring within 30 days or during hospitalization following the index procedure, unless there is evidence of accidental or self-inflicted death.

Death occurring within 30 days or during hospitalization following conversion to open repair or a secondary intervention for migration, Type I and III endoleaks, device integrity failure (e.g., fracture), or patency-related events (i.e., device stenosis or occlusion and embolic events), unless there is evidence of accidental or self-inflicted death;

Death occurring within 30 days or during hospitalization for a complication of the aneurysm or a complication associated with the device, such as:

- aortic rupture
- fistula formation (e.g., aorto-enteric)
- embolization
- malperfusion of organ(s) or limb(s)

Arterial fistula formation: formation of an abnormal connection or passageway between an artery and adjacent structures

Crawford Type IV TAAA: aneurysmal dilation originating within 5 cm of the celiac artery.

Conversion to Open, Early: any open repair within 30 days of the index procedure involving the vasculature in the abdomen and/or pelvis.

Conversion to Open, Late: any open surgical repair involving stent graft removal after 30days post index procedure

Chronic Obstructive Pulmonary Disease (COPD): forced expiratory volume (FEV1) < 1.0 liter or receiving home oxygen

Disabling stroke: Modified Rankin Score MRS >2

Distal landing zone: aortic fixation site furthest from the heart

Embolization: dislodging of an upstream particle that travels downstream causing blockage of free flow further downstream. Embolization could result in malperfusion

Embolus: blood clot that forms at one location (presumably from the aneurysmal sac, aortic neck, or adjacent vessels) and is dislodged to another location resulting in ischemic changes

Emergent: an aneurysm requiring immediate treatment

Endoleak:

Type I: leak occurring at the proximal or distal fixation site, including leakage around fenestrations

Type Ia: leak occurring at the proximal fixation zone of the stent-graft

Type Ib: leak occurring at the distal fixation zone of the stent graft

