Malperfusion of organ(s) or limb(s): loss of flow through a particular vascular bed has been partially or completely compromised leaving the said organ or limb ischemic

Migration, clinically significant: antegrade or retrograde migration that requires surgical or endovascular intervention

Paraparesis: spinal cord ischemic event resulting in partial neurologic deficit in the lower extremities

Parietal arteries (branches): inferior phrenic, lumbar and middle sacral arteries

Patency: the state of a vessel that has unimpeded flow into and out of the vessel

Proximal landing zone: the aortic fixation site closest to the heart

Proximal fixation length: the aortic fixation site measured from the proximal edge of the graft to the start of the aneurysm

Renal insufficiency: rise in serum creatinine of more than 50% above pre-procedure level which results in a serum creatinine >2.0 mg/dl that does not spontaneously resolve

Technical success:

- successful delivery (i.e., ability to deliver the implant to the intended implantation site, without the need for unanticipated corrective intervention related to delivery);
- successful and accurate deployment, defined as:
 - deployment of the endovascular stent-graft at the intended implantation site.
 - patency of all endovascular graft and stent components; absence of device deformations (e.g., kinks, stent eversion, mal-deployment, misaligned deployment) requiring unplanned placement of an additional device.
 - absence of inadvertent covering of aortic branch vessels; and
- successful withdrawal (i.e., successful withdrawal of the delivery system, without need for unanticipated corrective intervention related to withdrawal)

Thrombus: a blood clot that forms due to injury of a vessel. If the thrombus becomes dislodged and travels it is referred to as an embolus

Treatment success: a composite of technical success and freedom from the following:

- aneurysm enlargement i.e. >10-mm as compared to any previous CT measuring orthogonal (i.e., perpendicular to centerline) measurements

- aneurysm-related mortality
- aneurysm rupture
- conversion to open repair
- secondary intervention for migration, type I and III endoleaks, device integrity failure (i.e., fracture), and patency-related events (i.e., device stenosis or occlusion and embolic events)

Type B – Chronic Dissection: a dissection that takes off distal to the left subclavian artery that is greater than 30 days old

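### Sac enlargement is compared with any earlier CT, and scans older than the planning CT are not excluded, so growth before implant can be scored as treatment failure

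*Combined protocol and SAP*

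**What the plan says.** Freedom from aneurysm enlargement is part of treatment success, and the 1-year treatment-success proportion is the primary effectiveness endpoint. The enlargement criterion is stated four times:

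- Synopsis, primary endpoints: "Aneurysm enlargement i.e., greater than or equal to 5 mm as compared to any previous CT measure using orthogonal".
- Section 4.4.3: "Aneurysm enlargement i.e., greater than 5mm as compared to any previous CT measure using orthogonal".
- Section 4.9, entry for aortic aneurysm enlargement: "≥ 5 mm as compared to any previous CT measure using orthogonal (i.e., perpendicular to the centerline) measurements".
- Section 4.9, entry for treatment success: "aneurysm enlargement i.e. >10-mm as compared to any previous CT measuring orthogonal (i.e., perpendicular to centerline) measurements".

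The cut-offs differ, but the reference is the same each time, and none of the four says when the comparison scans may start. Table 5 (section 4.4.4) names no reference scan. Table 8 (section 4.7) asks for paired size data without saying which pair.

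One of the four alternative aneurysm criteria for entry in section 4.4.2 is "Aneurysm with a history of growth greater than or equal to 0.5 cm in 6 months". The list is introduced by "A patient may be entered into the study if the patient has at least one of the following", so growth can qualify a subject on its own. On natural history, section 3.2 says: "The expansion rate of thoracoabdominal aneurysms ranges from 2-4mm per year".

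**The concern.** Section 4.1 sets the effectiveness question as whether subjects reach treatment success and keep it for one year. Growth before the device was implanted says nothing about that. With an open reference, though, a scan from before enrolment can serve as comparator, and earlier growth then counts against the device. The growth entry criterion makes this concrete, because its 5 mm equals the failure cut-off in two of the four statements. Subjects entered on size after a period of surveillance are exposed in the same way.

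Neighbouring entries in 4.9 do have a time anchor. Renal insufficiency is judged against the level before the procedure, early and late endoleak are dated from deployment, and early conversion is dated from the index procedure. Enlargement has none. The component also feeds treatment success at every later visit. The data are to be pooled with parallel studies, so two sites applying the same words could classify the same subject differently.

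**Working it through.** The plan gives no sample size, margin or expected rate for the effectiveness endpoint, so there is no stated figure to reproduce. The check applies each written rule to a sac that is stable after repair.

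**Inputs.** Cut-offs: ≥5 mm (synopsis; 4.9 enlargement entry), >5 mm (4.4.3), >10 mm (4.9 treatment-success entry). Growth criterion: 0.5 cm = 5 mm in 6 months (4.4.2). Natural expansion: 2 to 4 mm per year (3.2). Subjects: 8 primary, 7 expanded, 15 in all (4.4).

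**Step 1: the rule.** Let g be the growth from an earlier orthogonal CT to the planning CT, and c the change from the planning CT to the 12-month CT. The measured difference is g + c. For a stable sac c = 0, so the difference is g.

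| g (mm), c = 0 | ≥5 mm | >5 mm | >10 mm |
|---|---|---|---|
| 5 | fail | pass | pass |
| 6 | fail | fail | pass |
| 10 | fail | fail | pass |
| 11 | fail | fail | fail |

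Example: 50 mm on an old CT, 55 mm on the planning CT and 55 mm at 12 months gives 55 − 50 = 5 mm. That is a failure at ≥5 mm only. With 50, 56 and then 54 mm, g + c = 6 − 2 = 4 mm, which passes under all three cut-offs.

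**Step 2: subjects entered on size.** At the protocol's own expansion rates, 5 mm accrues in 5/4 = 1.25 years to 5/2 = 2.5 years, and 10 mm in 10/4 = 2.5 years to 10/2 = 5 years. A CT older than that could trigger the rule, if it exists and is used.

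**Step 3: effect on the result.** One misclassified subject moves the proportion by 1/8 = 12.5 points (primary arm), 1/7 = 14.3 points (expanded arm) or 1/15 = 6.7 points (all subjects). The number affected is not given, so 0 to 2 is assumed here, with every other subject a success. Exact 95% intervals in the primary arm are:

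- 0 affected: 8/8 = 100% (63.1 to 100)
- 1 affected: 7/8 = 87.5% (47.3 to 99.7)
- 2 affected: 6/8 = 75.0% (34.9 to 96.8)

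On all 15 subjects, one affected gives 14/15 = 93.3% (68.1 to 99.8).

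**Step 4: after the change proposed below.** If no scan before the planning CT is admissible, a sac unchanged since that CT shows a difference of 0 mm and passes under every written cut-off.

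**The case against.** The best reply is that the plan means study scans only. Section 4.4.5.1 takes the sizing measurements, including maximum aortic diameter, from the pre-operative CT. The data-collection list in 4.6.1 does not mention re-measuring historical scans. The components are assessed at follow-up visits. In Table 8 the operative row appears to show size increase as not applicable, although column positions in the extracted table are not certain. This leans towards an on-study reading, but nothing says so, and the rule as written is wider.

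A reader might also infer more than the text supports:

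- *Every subject entered on growth is bound to fail.* No. A stable sac with 5 mm of earlier growth fails only at ≥5 mm, and shrinkage after repair can bring the difference below any cut-off.
- *Such a subject must have a qualifying earlier CT.* No. The growth criterion names neither CT nor orthogonal measurement, while the endpoint requires both.
- *The problem is the same at every cut-off.* No. The open reference can matter under all three, but at >10 mm only for earlier growth above 10 mm.
- *The pooled result will be biased by differences in old scans between sites.* This is possible, but the documents give no information on it.

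It is also fair to say that this is a 15-subject feasibility study and that effectiveness is reported as a count. The performance goal and power statement in 4.4.7 concern safety only.

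**Conclusion.** The point stands as a fault in the wording of a primary endpoint definition. All four statements admit scans from before the planning CT, so a subject with no sac growth after implant can be classified as a treatment failure. The rule is over-inclusive as stated, and nothing elsewhere in the plan narrows it.

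The conclusion rests on three conditions: an earlier orthogonal CT exists, it is used as comparator, and earlier growth net of any later shrinkage reaches the cut-off in force. How often all three hold cannot be worked out from the documents, so the sizes in the working are per subject and do not estimate the total error. With 8 subjects in the primary arm, one such case is visible in the headline proportion. No type I error or power figure is affected.

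**What to change.** In four places (synopsis, 4.4.3 and both 4.9 entries), replace the open reference with: the smallest orthogonal maximum diameter on the pre-operative planning CT or any later study CT. Add that older historical CTs are used for eligibility only. In the same edit, settle on one cut-off in place of ≥5, >5 and >10 mm.

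Starting at the first CT after repair, or after the completion procedure in a staged repair, would also remove the artefact. It would, however, drop enlargement between stages from the endpoint. Section 3.4.2.1 lists enlargement among the increased risks of staging, and completion of planned staging is targeted at 4 to 6 weeks. Starting at the planning CT avoids that loss. Using the smallest later diameter still catches a sac that shrinks and then regrows.

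The cost is a short text change and no new scans, since Table 5 already schedules pre-operative and follow-up CT. One small downside remains: growth between the planning CT and the implant still counts. The parallel studies should adopt the same wording so that the data can be pooled.

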3.3.2 Open Surgical Repair

Open repair of thoracoabdominal aneurysms, especially in patients with preexisting comorbidities, is fraught with complications. A meta-analysis of 7,833 open repairs of thoracoabdominal aneurysm repairs from 2000 to 2010 found a 30 day mortality rate of 7%, in-hospital mortality of 10%, spinal cord ischemia rates of 7.5%, renal failure rates of 19%, and pulmonary dysfunction rates of 36%¹³. Predictors of adverse events after elective open repair based on pre-existing comorbidities have been established. Advanced age (>70 years)^{14,17}, respiratory disease¹⁶, renal insufficiency¹⁸, coronary artery disease^{14,17}, symptomatic aneurysms, extent 1 and 2 aneurysms¹⁹⁻²², and diabetes²³ are reported to be a predictor of 30-day mortality. Cardiac function²⁴, extent 1 and 2 aneurysms^{20,25-27}, symptomatic cases²⁷, and diabetes²³ are reported to be predictors of paraplegia. The outcomes reported above are in a low- to moderate- risk patient population. It is a logical extension to assume the outcomes in moderate- to high- risk patients would be worse.

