4.1 Purpose

The primary objective of the clinical investigation is to assess the use of the VTAAA stent graft system to repair thoracoabdominal aortic aneurysms in patients having appropriate anatomy. The primary intent of the study is to assess safety (i.e. freedom from major adverse events (MAE) at 30 days) and preliminary effectiveness (i.e., treatment success and technical success) of the device (i.e., the proportion of treatment group subjects that achieve and maintain treatment success at one year).

Additionally, the study will assess technical success and treatment success at each follow-up interval.

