4.4.7 Data Presentation and Analysis Plan

The primary purpose of this study is to evaluate the safety of this device as there are no or very limited devices and clinical options available for this patient population. The primary safety endpoint of this study is safety freedom from major adverse events (MAE) at 30 days or during hospitalization if this exceeds 30 days. Major adverse events include death, bowel ischemia, myocardial infarction, paraplegia, renal failure, respiratory failure, and stroke. The primary safety endpoint will be analyzed to determine statistical significance when compared to a target performance goal. A literature review of outcomes of open surgical repair was used to create the performance goal as there is not a comparable endovascular option to use for analysis. The performance goal was selected based on the range of subjects experiencing a major adverse event at 30 days. The range was calculated based on assumptions of the minimum and maximum number of subjects experiencing at least one MAE in the historical open surgical repair group (Table 6). Based on the literature reviewed and the above assumptions the range of subjects experiencing at least one MAE in the open surgical repair group is 30.5% to 77.4%.

The primary effectiveness endpoint is the proportion of the study subjects with treatment success at 1 year. The data will be presented as quality outcomes with the number of study subjects with treatment success compared to the overall patient population.

Additionally, data outcomes from this study will be entered into a common vascular database so that data can be pooled with other PS-IDEs. This would provide consistent reporting across the PS-IDEs. Additionally, the PS-IDEs will be evaluating the same device and endpoints to allow for a poolability of data across the sites.

The pooled data will be separated into two separate study arms: primary study arm and expanded selection arm.

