4.4.7.1 Statistical Methods

The primary hypothesis of the Visceral Manifold Study is the number of subjects experiencing a major adverse event through 30 days will be less than a target performance goal (PG) of 50%. The PG was determined by using a conservative target that is approximately the average of the open surgical repair MAE rate calculated above (30.5%-77.4%, Table 6). The anticipated test device 30-day MAE rate was based on the current rate of MAE's (26%, Table 7) observed in 20 subjects meeting inclusion criteria into the primary study as of June 2016.

The sample size for the Visceral Manifold Study was determined using an exact method based on a one-sided 2.5% significance level and an anticipated 26% investigational device 30-day major adverse event rate. Based on these assumptions, a sample size from the pooled PS-IDE data of 46 subjects provides at least 80% power to test the primary hypothesis.

Table 6. Historical Comparison for Primary Safety Endpoint (MAE Rate at 30 days for Open Repair)

Reference	# of Patients	Mortality	Bowel Ischemia	Myocardial Infarction	Paraplegia	Renal Failure	Respiratory Failure	Stroke
Rigberg et al	1010	191 (19%)						
Becquemin et al	1678	90 (5.4%)	51 (3%)	20 (1.2%)	16 (1%)	289 (17.2%)	124 (7.4%)	12 (0.7%)
Murana et al	542	46 (8.5%)			22 (4.2%)			
Ferrer et al	257	16 (6.2%)			53 (20.8%)	31 (12.3%)	31 (12.3%)	
Bensley et al	450	45 (10%)		10 (2.4%)		48 (10.7%)	202 (45.1%)	9 (2.2%)
Nathan et al	83	6 (5.6%)						
Dayama et al	682	68 (10%)		87 (12.9%)		117 (17.2%)	286 (42%)	

Ferrante et al	200	5 (2.5%)		25 (12.8%)		22 (11%)	27 (13.8%)	
Tsilimparis et al	1091	58 (5.4%)		87 (8%)		109 (10%)	229 (21%)	
Piazza et al	7833	1331 (17%)			587 (7.5%)	1488 (19%)	2819 (36%)	
Total	13826	1855/13826	51/1678	229/4101	678/10310	2104/12191	3718/12191	21/2128
Rate of MAE at 30 Days for Open Surgical Repair		13.4%	3.0%	5.6%	6.6%	17.3%	30.5%	1.0%

Table 7. Historical Comparison for Expected Investigational Device 30 Day MAE Rate (Outcomes of subjects treated with the VTAAA stent graft system and meeting inclusion into the primary study as of June 2016)

Dataset	Mortality	Bowel Ischemia	Myocardial Infarction	Paraplegia	Renal Failure	Respiratory Failure	Stroke
Subjects meeting VMS PS-IDE I/E criteria	0/20 (0%)	0/20 (0%)	0/20 (0%)	2/20 (9.5%)	1/20 (5%)	3/20 (14%)	0/20 (0%)

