Type Ic: leak occurring at the distal fixation zone of the covered stents in the visceral vessels incorporated by the fenestrations

Type II: leak caused by retrograde flow from patent lumbar or inferior mesenteric arteries

Type IIIa: leak caused by a defect in the graft fabric

Type IIIb: leak caused by inadequate seal between modular graft components

Type IV: leak caused by graft fabric porosity, often resulting in a generalized blush of contrast within the aneurysm sac

Endoleak, Early: any endoleak observed within 30 days after device deployment

Endoleak, Late: any endoleak observed later than 30 days after deployment that was not documented during the first 30 days after deployment

Estimated Glomerular Filtration Rate (eGFR): estimated GFR (mL/min/1.73 m²) = 175 x (Serum creatinine)^{-1.154} x (Age)^{-0.203} x (0.743 if female) x (1.210 if African American)

Graft Relining: placement of the investigational system that results in landing zones that extend beyond the limits of the previously placed graft material

Limb occlusion: the presence of thrombus within any graft limb that creates occlusion

Major adverse events: all-cause mortality, bowel ischemia (requiring medical or surgical management), myocardial infarction, paraplegia, renal failure, respiratory failure, and stroke

- **All-Cause Mortality:** any death occurring within the first 30 days post procedure

- **Bowel Ischemia:** Bowel ischemia due to limb or arterial occlusion, graft placement, or embolization.
- **Myocardial infarction:** raised levels of cardiac biomarkers or ECG changes
- **Paraplegia:** spinal cord ischemic event resulting in complete loss of motor function with or without loss of sensation in the lower extremities
- **Renal Failure:** acute or progressive renal insufficiency leading to the need for dialysis or hemofiltration
- **Respiratory failure:** prolonged intubation (>48 hours after spinal drain removal or >72 hours total) and/or reintubation. This definition does not put the patient at any increased risk. The high-risk patient population being treated in this study is prone to pre-existing comorbidities, including COPD and decreased respiratory function, and may require extended ventilator support while in the supine position for spinal drainage.
- **Stroke:** neurological deficit that lasts > 24 hours

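### The primary safety endpoint runs past day 30 for subjects still in hospital, but the tested hypothesis, the objective and the 4.9 definition of death as an MAE stop at 30 days

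*Combined protocol and SAP*

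**What the plan says.** Section 4.4.3 states: "The primary safety endpoint is freedom from major adverse events (MAE) at 30 days or during hospitalization if this exceeds 30 days". The synopsis has the same rule, and the analysis plan in 4.4.7 repeats it: "safety freedom from major adverse events (MAE) at 30 days or during hospitalization if this exceeds 30 days". In each place death is listed as an MAE with no time limit of its own.

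Three other parts of the document are narrower.

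- **Hypothesis (4.4.7.1):** the claim to be tested is that "the number of subjects experiencing a major adverse event through 30 days will be less than a target performance goal" of 50%.
- **Objective (4.1, repeated in the synopsis):** the intent is to "assess safety (i.e. freedom from major adverse events (MAE) at 30 days".
- **Definition (4.9):** under major adverse events, all-cause mortality is "any death occurring within the first 30 days post procedure". The six non-fatal components have no such limit. In the same section, aneurysm-related mortality does extend to the hospital stay: "Death occurring within 30 days or during hospitalization following the index procedure".

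No section says which wording takes precedence.

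**The concern.** The primary safety endpoint is the only endpoint in the plan with a formal test, and its window is written in two ways. The difference concerns subjects who stay in hospital beyond 30 days, which can follow a complicated repair. Two separate conflicts arise.

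The first is confined to death. 4.9 is the only place where the MAE components are defined, and it puts a time limit on death alone. Followed literally, an in-hospital stroke on day 40 is an MAE and an in-hospital death on day 40 is not.

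The second touches all seven components. The 4.4.7.1 hypothesis stops at 30 days, so the quantity tested against the 50% goal is not quite the endpoint defined in 4.4.3.

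At stake is whether a serious late in-hospital event counts against the device in the main safety result. If this is not settled beforehand, it would be decided after the event is known, and possibly in different ways by the studies that contribute to the pooled test.

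**Working it through.** **1. The plan's own figure.** Inputs from 4.4.7.1: exact test, one-sided 2.5%, goal p0 = 0.50, anticipated rate p1 = 0.26, pooled n = 46. Let X be the number of subjects with an MAE. The goal is met if X ≤ c, where c is the largest count with P(X ≤ c | 46, 0.50) ≤ 0.025.

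- P(X ≤ 15 | 46, 0.50) = 0.0129 and P(X ≤ 16 | 46, 0.50) = 0.0270, so c = 15.
- Power = P(X ≤ 15 | 46, 0.26) = 0.881.

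The statement of at least 80% power is correct. The window problem does not make the sample size wrong.

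**2. The rules applied to the same subjects.** The columns show whether each text, read literally, counts the subject as having an MAE.

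| Subject | 4.4.3 and 4.4.7 | 4.9 definition | 4.4.7.1 hypothesis |
|---|---|---|---|
| Death before day 30 | yes | yes | yes |
| Non-fatal MAE before day 30, in-hospital death on day 40 | yes | yes (non-fatal event) | yes (non-fatal event) |
| Still in hospital, first stroke on day 40 | yes | yes (no time limit) | no |
| Still in hospital, death on day 40, no other MAE | yes | **no** | no |
| Discharged without an MAE, death after day 30 | no | no | no |

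The rules part only in the third and fourth rows. The 4.9 limit matters only in the fourth, because a subject with any non-fatal MAE is already counted under 4.9. The 4.4.7.1 wording matters in both.

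**3. What one subject is worth.**

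- Primary arm of this study: 1/8 = 12.5 points.
- Pooled test: 1/46 = 2.2 points.

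**4. What the wider window could do to power.** The 26% and Table 7 (0 deaths in 20) are labelled 30-day, and the documents give no rate of first MAE after day 30 in hospital. Suppose the wider window adds d points to 26%. This range is assumed. Power = P(X ≤ 15 | 46, 0.26 + d):

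| d (points) | 0 | 1 | 2 | 3 | 5 |
|---|---|---|---|---|---|
| Power | 88.1% | 84.7% | 80.7% | 76.2% | 66.0% |

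The stated 80% survives an addition of up to 2 points.

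**The case against.** The best reply is that the endpoint text is self-contained. Three sections give the same window and list plain death, and none points to 4.9. Against them stands one entry in a list of definitions. That entry looks like a drafting slip: it is the document's only definition of all-cause mortality, yet it could not serve the secondary endpoint of all-cause mortality at each follow-up interval. This stands as evidence of intent, and it is why the fix adopts the 4.4.3 window. It is not a written rule of precedence, and it leaves the hypothesis untouched.

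It is also fair to say that few subjects will be affected. Someone who dies after more than 30 days in hospital may well have had another MAE already, given that 4.9 counts any reintubation as respiratory failure. Nor is the death lost. Unless accidental or self-inflicted, it counts as aneurysm-related mortality and so fails the effectiveness composite, and the DSMB reviews it. Both points stand.

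One could instead hold everything to 30 days, which would match the labels on Tables 6 and 7. That would be consistent, but it would drop the window that the protocol states three times for its primary endpoint.

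A reader might infer three stronger things, which the documents do not support.

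- **That the 4.9 wording could reverse the pooled result.** One more event at the boundary does turn 15/46 (p = 0.0129, met) into 16/46 (p = 0.0270, not met). That is true of any single reclassified subject and does not measure this defect. Moreover, correcting 4.9 alone cannot move the test while 4.4.7.1 stops at 30 days.
- **That about 1.4 of the 46 subjects would be affected.** For open repair, 3.3.2 reports that a meta-analysis "found a 30 day mortality rate of 7%, in-hospital mortality of 10" percent, and 3 points × 46 = 1.38. This is not a device rate, it assumes a common denominator, and it includes subjects with another MAE.
- **That the sample size is wrong.** It is not, as the first step of the working shows.

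**Conclusion.** The inconsistency is real and lies in the current text. The endpoint statements (synopsis, 4.4.3, 4.4.7) include a hospital stay beyond 30 days. The hypothesis and the objective do not, for any component, and 4.9 separately excludes later deaths. Read literally, a day-40 in-hospital death with no other MAE fails the endpoint under 4.4.3 and is not an MAE under 4.9. Any first MAE after day 30 of a prolonged stay is outside the 4.4.7.1 test.

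The number of such subjects is unknown and probably small. The conclusion rests on the literal wording of each section and on the absence of any rule of precedence. It assumes nothing about how often such events occur. It should be settled before outcomes are scored, because it defines what counts in the primary safety result.

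Table 6 gives 17% mortality for its 7,833-patient row, where 3.3.2 and 3.4.1 give 7% at 30 days and 10% in hospital for a series of that size. That is a separate matter with no bearing on which window governs, and it should be raised as its own point.

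**What to change.** Use the 4.4.3 window throughout.

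- Add its extension to a longer hospital stay in four places: the MAE all-cause mortality definition in 4.9, the hypothesis in 4.4.7.1, and the objective in both the synopsis and 4.1.
- Keep the individual MAE components as 30-day secondary endpoints, as 4.4.3 already has them.
- Tabulate the fixed 30-day MAE rate beside the primary result, because Tables 6 and 7 and the 26% planning rate are labelled 30-day.

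The cost is one phrase in four places and one extra tabulation, with no change to the sample size. The tested rate may be slightly less favourable, with the power consequences shown in the working. The test uses data pooled with other physician-sponsored studies, and 4.4.7 says these evaluate the same endpoints. The same window therefore has to apply in all of them. Their protocols are not among these documents, so this needs to be confirmed.
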